**FRED HUTCHINSON CANCER RESEARCH CENTER
 UNIVERSITY OF WASHINGTON SCHOOL OF MEDICINE
 SEATTLE CHILDREN'S**

Current version: 7/07/2021

Previous version: 1/12/2021

Title of Protocol:

A randomized trial for patients with high-grade myeloid neoplasms with measurable residual disease (MRD): CPX-351 vs. immediate allogeneic hematopoietic cell transplantation

Investigators List:

Investigator	Professional Title	Phone Number
[name], MD	Associate Professor, FHCRC; Assistant Professor of Medicine, UW	[contact]
[name]	Assistant Professor, FHCRC; Assistant Professor of Medicine, UW	[contact]
[name]	Acting Instructor, UW	
[name]	Professor, FHCRC; Professor of Medicine, UW	[contact]
[name] PhD MS	Associate Professor, FHCRC; Associate Professor of Medicine, UW	[contact]
Biostatistician:		
[name]	Professor, FHCRC; Affiliate Professor of Biostatistics, UW	[contact]
Research Staff:		
[name]	Clinical Research Coordinator, Fred Hutch	[contact]
[name]	Clinical Research Coordinator, Fred Hutch	[contact]
[name]	Data Coordinator, Fred Hutch	[contact]
[name], MS	Research Administrator, Fred Hutch	[contact]

Study Regimen: AML/MDS-EB2 patients with measurable residual disease randomized to either immediate hematopoietic cell transplantation vs. treatment with up to 2 courses of CPX-351 prior to hematopoietic cell transplantation.

IND HOLDER: [name], PhD

IND Number: 152141

FHCRC Emergency (24 hour) [contact]; [contact]

PROTOCOL SYNOPSIS

Protocol Title	A randomized trial for patients with high-grade myeloid neoplasms with measurable residual disease (MRD): CPX-351 vs. immediate allogeneic hematopoietic cell transplantation (alloHCT)
Protocol Number	RG1007476
Protocol Sponsor	[name], PhD
IND Number	152141
Trial Phase	Phase II
Trial Type	Interventional
Clinical Indication	Patients with detectable leukemia following intensive chemotherapy
Study Objectives	To determine whether treatment with CPX-351 improves outcomes over immediate allogeneic transplantation among patients with measurable residual disease following intensive chemotherapy.
Study Design	Eligible AML/MDS-EB2 patients with MRD will be enrolled and randomized to either immediate allogeneic hematopoietic cell transplantation vs. treatment with CPX-351 for 1-2 courses prior to allogeneic hematopoietic cell transplantation.
Population	Acute Myeloid Leukemia (AML) and Myelodysplastic Syndrome (MDS)-EB2
Primary Endpoints	Overall survival
Secondary Endpoints	
Among all patients:
 
 • Relapse-free survival • relapse • non-relapse mortality • rate of transplantation • type of transplant (myeloablative, reduced intensity) 
Among patients treated with CPX-351:
 
 • frequency of MRD prior to transplantation • changes in leukemia-associated mutations prior to transplantation
Type of control	Active Treatment
Investigation Drug	CPX-351 (Daunorubicin and Cytarabine) Liposome for Injection
Dose	Daunorubicin 44 mg/m² and cytarabine 100 mg/m², days 1,3,5 of a 28-day cycle. Patients may receive up to two courses of CPX-351 to be given on days 1 and 3 of the second cycle.
Route of administration	Intravenous
Transplant Conditioning Regimens	Various for patients receiving allogeneic hematopoietic cell transplantation
Trial Blinding	Not Blinded
Treatment Groups	
ARM A – Early allogeneic transplantation without MRD directed therapy.
 
Patients assigned to ARM A will be treated with allogeneic transplantation without intervening chemotherapy according

	
to established treatment protocols and at the direction of their physician.
 
ARM B – CPX-351 followed by allogeneic transplantation. Patients assigned
 
to ARM B will receive CPX-351 (Daunorubicin and Cytarabine) Liposome for Injection at a dose of daunorubicin 44 mg/m² and cytarabine 100 mg/m² via intravenous infusion over 90 min on days 1, 3, and 5. Patients may receive up to two courses of CPX-351. Patients may receive subsequent allogeneic transplantation at the discretion of their physician.

Treatment Schedule	
Among patients randomized to ARM A – Transplantation will be initiated by the treating physician.
 
Among patients randomized to ARM B – CPX-351 will be administered on days 1,3, and 5. Patients may receive up to two courses of CPX-351 with the second course given on days 1 and 3 only. CPX-351 is followed by allogeneic transplantation at the discretion of the treating physician.

Efficacy Assessments	
Treatment response (e.g. CR without MRD, CR, CRi, morphologic leukemia-free state [MLFS], partial remission [PR]) or treatment failure (e.g. refractory disease, death in aplasia, death from indeterminate cause, hematologic relapse, molecular relapse) as well as treatment outcome (e.g. overall survival, relapse-free survival, event-free survival, and remission duration) will be determined by peripheral blood count and bone marrow evaluation and categorized according to the 2017 European LeukemiaNet criteria.(Döhner et al., 2017)

Number of trial subjects	130
Estimated duration of trial	5 years
Duration of Participation	2 years following enrollment. Additional demographic details (survival) following 1yr.

ABBREVIATIONS

AML	Acute myeloid leukemia
ATG	Anti-thymocyte globulin
BM	Bone marrow
CLIA	Clinical Laboratory Improvement Amendment
CPX-350	Cytarabine and daunorubicin
CR	Complete remission
CRI	Complete remission with incomplete hematologic recovery
CTCAE	NCI Common Terminology Criteria for Adverse Events
DLI	Donor lymphocyte infusion
DLT	Dose-limiting toxicity
FLAG	Fludarabine, cytarabine, G-CSF
FLAMSA	Fludarabine, amsacrine, and cytarabine
FHCRC	Fred Hutchinson Cancer Research Center
G-CLAC	G-CSF, clofarabine, and cytarabine
GVHD	Graft-versus-host disease
GVL	Graft-versus-leukemia
HCT	Hematopoietic cell transplantation
HLA	Human leukocyte antigen
LFS	Leukemia-free survival
MEC	Mitoxantrone, etoposide, and cytarabine
MLFS	Morphologic leukemia-free state
MMF	Mycophenolate mofetil
MRD	Measurable ('minimal') residual disease
NMDP	National Marrow Donor Program
MTD	Maximum tolerated dose
NCI	National Cancer Institute
OS	Overall survival
PBSC	Peripheral blood stem cells
RIC	Reduced-intensity conditioning
R/R	Relapsed/refractory
SCCA	Seattle Cancer Care Alliance
TBI	Total body irradiation
TRM	Treatment Related Mortality
UW(MC)	University of Washington (Medical Center)

Table of Contents

1.0	GENERAL INFORMATION	7
1.1	Title: A randomized trial for patients with high-grade myeloid neoplasms with measurable residual disease (MRD): CPX-351 vs. immediate allogeneic hematopoietic cell transplantation	7
1.2	Funding information: The study will be funded by Jazz Pharmaceuticals	7
1.3	Investigator information: The study will be conducted within the Cancer Consortium, based at Fred Hutchinson Cancer Research Center.	7
2.0	INTRODUCTION TO THE PROTOCOL	7
2.1	Introduction	7
2.2	AML with MRD	7
2.3	CPX-351	9
2.4	Dose Rationale	9

1.0 GENERAL INFORMATION

- 1.1 Title:** A randomized trial for patients with high-grade myeloid neoplasms with measurable residual disease (MRD): CPX-351 vs. immediate allogeneic hematopoietic cell transplantation
- 1.2 Funding information:** The study will be funded by Jazz Pharmaceuticals.
- 1.3 Investigator information:** The study will be conducted within the Cancer Consortium, based at Fred Hutchinson Cancer Research Center.

2.0 INTRODUCTION TO THE PROTOCOL

2.1 Introduction

Acute myeloid leukemia (AML) is a disease that is fatal within the first few weeks or months after diagnosis if left untreated. Intensive induction chemotherapy soon after diagnosis is the most common treatment for fit patients and should be considered regardless of patient's age according to the 2017 European LeukemiaNet (ELN) guidelines. (Döhner et al., 2017) Though most patients will achieve a complete remission (CR), defined as morphologic blast count in the bone marrow <5% coupled with peripheral count recovery, most will ultimately relapse. Allogeneic hematopoietic cell transplantation (alloHCT) offers a chance to decrease the relapse risk in many patients.

2.2 AML with MRD

2.2.1 Detection of MRD

The 2017 ELN guidelines single out a new response category of CR without measurable residual disease (MRD) applicable to patients with a demonstrable marker of disease prior to treatment that is no longer detectable after treatment (e.g., a flow cytometric immunophenotype, a molecular marker that can be followed by quantitative polymerase chain reaction or next generation sequencing, or abnormal karyotype identified through conventional cytogenetics or fluorescence *in situ* hybridization). (Döhner et al., 2017) Sensitivities of the methodologies differ based on the characteristics of the individual tests and their operators as well as the characteristics of an individual patient's leukemic blasts.(Grimwade & Freeman, 2014) In 2018, the ELN published consensus recommendations regarding MRD monitoring in AML, suggesting that central laboratories with significant experience in the different methodologies perform testing whenever possible.(Schuurhuis et al., 2018)

Notably, an individual patient may have MRD detectable by one method but not another. One analysis suggested that discordance between flow and cytogenetic detection of MRD was found in 22% of patients; most importantly, however, detection of MRD by any means was a negative prognostic marker.(Fang et al., 2012) Detection of certain molecular abnormalities can be predictive of relapse, while persistence of others after chemotherapy (the so-called DTA mutations, including *DNMT3A*, *TET2*, and *ASXL1*) is not.(Jongen-Lavencic et al., 2018)

2.2.2 Predictive significance of MRD

The best treatment strategy for patients who achieve a CR after induction but have persistent MRD is not clear. Such patients with detectable flow, molecular, or cytogenetic abnormalities have a higher likelihood of relapse than those who obtain CR without MRD after induction therapy.(X. Chen et al.,

2015; Y. Chen et al., 2011; Freeman et al., 2013; Marcucci et al., 2004; Othus et al., 2016; Terwijn et al., 2013) Patients not receiving HCT had an 80% probability of relapse within 1 year if a conventional complete response (CR) was accompanied by MRD vs. 20% if it was not.(X. Chen et al., 2015) Though alloHCT may be curative in some such patients, the presence of pre-HCT MRD is indicative of worse outcomes post-transplant, with particularly poor relapse-free survival.(Mortland et al., 2013; Walter, Gooley, et al., 2011; Walter et al., 2015) Araki et al. observed patients receiving HCT in morphologic remission accompanied with MRD had rates of relapse, relapse-free survival, and survival at 1 year of 60%, 20%, and 30-40% respectively, significantly worse compared to those seen in patients in morphologic remission without MRD (15%, 75% and 80% respectively).(Araki et al., 2016)

Some pediatric AML investigators have proposed “risk adapted” strategies, which refine treatment in light of response to initial therapy,(Rubnitz et al., 2010) but these methods have not been widely adopted in adult AML. Additionally, no therapy has yet been shown to reliably and effectively eradicate MRD, either pre- or post-HCT. It should be noted that few studies have specifically targeted the MRD-positive population, though many are ongoing or planned since this is such a difficult population to treat.(Percival & Estey, 2019)

Eradication of MRD pre-HCT has the potential to improve post-HCT outcomes.

2.2.3 Eradication of MRD at FHCRC/UW

[figure not shown]
Attempts to reduce MRD in patients with AML at FHCRC/UW have been largely unsuccessful. A recent retrospective analysis by [name] found that MRD, generally present after one course of intensive initial induction, was eliminated in 10/28 patients (36%; 95% CI 19-56%) given additional intensive chemotherapy, and remained in all 21 patients given a less intense treatment as first attempt to eliminate MRD.(Appelbaum et al., 2019) Furthermore, it is unclear whether reduction of MRD will *per se* improve post HCT outcome. [name] analysis identified 16 patients subsequently transplanted (7 of 16 in CR/CRp) of whom only 2 survived longer than 1 year, with survival similar regardless of whether MRD was eliminated (7 pts) or not (9 pts) by chemotherapy.

If MRD is resistant to elimination or if its disappearance is irrelevant, it may be preferable to proceed directly to HCT despite the deleterious influence of pre-HCT MRD on post HCT outcome. [name] review found survival from the time of initial chemotherapy was longer in the 80 patients who received HCT as first treatment for MRD than in the 49 who received chemotherapy (**figure 1A**, median 13.8 mos. vs 11.6 mos., $p = 0.01$). Survival was not statistically different in the 16/49 patients who received HCT after first receiving chemotherapy than in the 80 patients who received HCT as first therapy for MRD despite the “guarantee time” the 16 enjoyed. Furthermore, survival dated from HCT was shorter in the 16/49 patients who received chemotherapy followed by transplant than in those given HCT as initial treatment for MRD (**figure 1B**, $p= 0.02$, I median 4.4 vs. 10.4 mos.) Regardless of elimination of MRD only 2 of the 16 (12.5%, 2-38%) survived longer than 1 year vs. 23 of the 80 (29%, 19-40%) given HCT without a prior attempt to eliminate MRD.

FIGURE 1. Panel A: Survival from start of initial treatment for MRD: chemotherapy 49 patients, HCT without prior effort to eliminate MRD 80 patients, no treatment 84 patients. **Panel B:** Survival from HCT in 16 patients who received chemotherapy to eliminate pre-HCT MRD and in 78 patients who went directly to HCT (no prior attempt to reduce MRD)

A)

B)

If efforts to reduce pre-HCT MRD were only intermittently successful, and if reduction was irrelevant, such efforts would serve only to delay HCT, if for example infectious complications arose; indeed, as noted above, only 16/49 patients who received chemotherapy to reduce MRD prior to HCT subsequently received HCT. Alternatively, attempts to reduce pre HCT MRD might make successful HCT less likely if, for example, blast numbers increased during the delay. This possibility might partially explain the infrequency (16/49) with which patients who initially received therapy to reduce MRD subsequently received HCT.

However, the above data were collected retrospectively with a variety of different induction attempts. These limitations motivate the planned clinical trial. Patients with high-grade myeloid neoplasms who have MRD will be randomized between two approaches: direct to alloHCT (Arm A) vs. treatment to eliminate MRD followed by alloHCT (Arm B).

2.3 CPX-351

CPX-351 (brand name Vyxeos) is a liposomal formulation of cytarabine and daunorubicin at an optimal, fixed molar ratio. The drug was approved by the Food and Drug Administration in 2017 for treatment of secondary AML in patients aged 60-75. Approval was based on a longer survival and event-free survival with CPX-351 in a trial randomizing such patients between standard 7+3 and CPX-351.(Lancet et al., 2018) Of particular interest is the disproportionately better survival with CPX-351 than 7+3 considering only patients receiving HCT (HR 0.46, 95% CI 0.24-0.89) than considering all patients (HR 0.69, 95% 0.52-0.90).(Lin et al., 2018) Possible explanations for the improved survival outcomes for patients after CPX-351 include HCT's greater sensitivity to an absence of MRD and a distinctive ability of CPX-351 to reduce MRD.

2.4 Dose Rationale

For patients randomized to Arm B of the clinical trial, they will receive induction dosing of CPX-351 at 100 units/m² on days 1, 3, and 5 of a 28-day cycle. Patients may receive up to two courses of CPX-351. Patients who receive the second course will receive induction dosing of CPX-351 at 100 units/m² on days 1 and 3 of a 28-day cycle.

2.5 Other Agents

This protocol will be an umbrella protocol in terms of HCT regimens. That is, patients randomized to Arm A (direct to HCT) or patients in Arm B who receive CPX-351 and then undergo HCT will be able to

receive any HCT regimen deemed appropriate by the treating physician including myeloablative or reduced intensity conditioning.

2.6 Risks/Benefits

AlloHCT carries inherent risks, including infection, graft-versus-host disease, and relapse of the original disease. Simultaneously, however, alloHCT represents the best chance of cure for many patients with AML and high-grade myeloid neoplasms. The goal of this clinical trial is to optimize the chance of post-HCT success for patients with evidence of pre-HCT MRD.

3.0 OVERVIEW OF CLINICAL TRIAL

3.1 Study Objectives

3.1.1 Primary Objectives

To determine whether treatment with CPX-351 improves overall survival over immediate alloHCT among patients with MRD following intensive chemotherapy.

3.1.2 Secondary Objectives

- To determine whether treatment with CPX-351 improves **relapse-free survival** over immediate alloHCT among patients with MRD following intensive chemotherapy.
- To measure the **rate of transplantation** following treatment with CPX-351 among patients with MRD following intensive chemotherapy.
- To determine whether treatment with CPX-351 improves **non-relapse mortality** over immediate alloHCT among patients with MRD following intensive chemotherapy.
- To compare, among patients with MRD following intensive chemotherapy, the frequencies of **types of transplant** received following treatment with CPX-351 vs. immediate transplantation.
- To measure the **frequency with which the burden of disease is decreased or eliminated** following treatment with CPX-351 among patients with MRD following intensive chemotherapy.

3.2 Study Population

[figure not shown]
Adults with high grade myeloid neoplasms and MRD following intensive chemotherapy with an intent to undergo alloHCT are invited to participate.

3.3 Study Design

This study is a phase II open-label randomized trial for patients with high-grade myeloid neoplasms with MRD following intensive chemotherapy, evaluating the efficacy of immediate alloHCT(ARM A) versus treatment with CPX-351 followed by alloHCT (ARM B). We intend to enroll 130 patients in order to treat 65 patients with alloHCT and 65 patients with CPX-351 followed by alloHCT.

Patients will have already received one cycle of intensive chemotherapy and remain MRD positive within 90 days of treatment. Patients must have an identified donor available prior to study enrollment.

SCHEMA

3.3.1 Primary Endpoint

The primary endpoint of the study is survival from the time of randomization. The survival (in days) of subjects in the two arms will be compared using the log-rank test.

3.3.2 Secondary Endpoints

- **Relapse-free survival** from the time of MRD identification and (among patients transplanted) from the time of transplantation. The following comparisons will be made: (1) number of days elapsing between the date of MRD identification and the date of death or relapse, (2) among transplanted patients, the number of days elapsing between the date of transplantation and the date of death or relapse.
- **Rate of transplantation** following treatment with CPX-351 among patients with MRD following intensive chemotherapy. The proportion of patients having begun transplant conditioning 60 days and 180 days following enrollment will be compared using the chi-squared test. The **time to transplant** among the two arms will be compared by comparing the number of days elapsed between enrollment and the initiation of transplant conditioning by the log-rank test.
- Frequencies of the **types of transplant** received. Among the patients receiving transplantation, the proportion of patients in each arm receiving myeloablative transplant conditioning will be compared using the chi-squared or Fisher's exact test. Among patients receiving transplantation, the proportion of patients in each arm receiving donor stem cells from a haploidentical donor, an unrelated donor, or from cord blood unit will each be compared using the chi-squared or Fisher's exact test.

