8.2 Administration of allogeneic transplantation (ARM A)

Following randomization patients in treatment **ARM A** will be referred for alloHCT. The transplant regimen and the timing of its initiation will be at the discretion of the transplant physician.

As soon as potential patients are identified for this protocol, the treating physician or the study staff will initiate the process of identifying an appropriate source of donor stem cells and a suitable transplant regimen. It is the intent of the study that patients randomized to treatment ARM A begin transplant conditioning within 45 days of randomization.

Any transplant regimen is allowed. The treating physician will indicate the donor stem cell type (matched related, matched unrelated, mismatched unrelated, haploidentical, or cord blood) as well as the transplant conditioning regimen and transplant conditioning regimen intensity (myeloablative vs reduced intensity) via questionnaires.

The specific evaluations, medications and procedures conducted during the course of the allogeneic transplant will be managed by the treating physician and may include experimental protocols and/or medications available at the treating institution.

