8.3 Administration of CPX-351 (ARM B)

Patients randomized to treatment ARM B will be treated with CPX-351 prior to alloHCT. Below is a sample timeline for subjects randomized treatment **ARM B**:

ARM B Treatment Schedule	
Day	Treatment
1	CPX-351 (daunorubicin 44 mg/m² and cytarabine 100 mg/m²) IV over 90 min
3	CPX-351 (daunorubicin 44 mg/m² and cytarabine 100 mg/m²) IV over 90 min
5	CPX-351 (daunorubicin 44 mg/m² and cytarabine 100 mg/m²) IV over 90 min
14 - 35	Bone marrow aspirate and biopsy*
≤60	CPX-351 cycle 2 OR allogeneic HCT

For patients assigned to **ARM B**, a second cycle of CPX-351 may be given at the discretion of the treating physician. In the event that a patient receives a second cycle of CPX-351, the expected time frame for start of HCT conditioning regimen will be considered within 60 days from CPX-351 Cycle 2, Day 1.

ARM B Treatment Schedule Cycle 2	
Day	Treatment
1	CPX-351 (daunorubicin 44 mg/m² and cytarabine 100 mg/m²) IV over 90 min
3	CPX-351 (daunorubicin 44 mg/m² and cytarabine 100 mg/m²) IV over 90 min
14 - 35	Bone marrow aspirate and biopsy*
≤60	Allogeneic HCT

If hypersensitivity or infusion-related reactions occur, infusion of CPX-351 may be prolonged to two hours (120 minutes) or more.

For patients assigned to **ARM B**, allogeneic transplant should be considered following either one or two cycles of CPX-351. The timing of transplantation (defined as start of transplant conditioning regimen) should be scheduled within 60 days of the most recent cycle of chemotherapy, unless delay is judged to be in the patient's interest by the transplant physician.

*Timing of bone marrow aspirate and biopsy procedures: The timing of the marrow evaluation is flexible and should occur not prior to 14 days and not later than 35 days following initiation of treatment, with a preference for the sample to be collected within 1 week of the count recovery (defined as two complete blood counts showing an absolute neutrophil count of $\geq 1,000/\mu\text{L}$ and a platelet count of $\geq 100k/\mu\text{L}$). If count recovery has not occurred prior to day 28, a marrow aspirate should be completed prior to day 35.

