11.0 TOXICITY MONITORING

11.1 Toxicity criteria

This protocol will conduct safety monitoring throughout the study for the CPX arm. The immediate alloHCT arm will not have monitoring specific to this trial, as these patients will be treated either on a HCT protocol which will monitor toxicity or on an HCT treatment plan. It is not expected that CPX will

lead to excessive toxicity as it has been studied in hundreds of patients. However, it is possible that use of CPX could lead to an unacceptable fraction of patients who do not proceed to transplant or in whom transplant is delayed (defined as start of transplant conditioning regimen more than 60 days following start of CPX) due to toxicity attributable to CPX. Therefore, the CPX arm will be monitored carefully for toxicity and inability for or delay in individual patients to proceed to HCT. Details are provided in Section 17. In addition, safety concerns associated with CPX will be identified by continuous review of the data by the Principal Investigator. The Principal Investigator will review the outcome of the data for each individual patient on an ongoing basis, and the Principal Investigator will have primary responsibility for ensuring that the protocol is conducted as approved by the Fred Hutchinson Cancer Research Center's Scientific Review Committee and Institutional Review Board. The Principal Investigator will also comply with the Fred Hutch Data and Safety Monitoring Plan as described beneath the Data and Safety Monitoring Plan section. The PI will personally review with the Research Nurse the clinical course of all the enrolled patients at least weekly.

All patients who receive CPX are evaluable for toxicity. Patients are evaluated from first day receiving study treatment until death, start of conditioning for HCT, or 56 days following the conclusion of treatment.

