17.2 Primary/Secondary Endpoints, Objectives and Analytical Methods

The primary endpoint of the study is overall survival from the time of randomization. The survival (in days) of subjects in the two arms will be compared using the stratified log-rank test (stratified on number of chemotherapy cycles and disease risk, factors that randomization is stratified on). Patients still alive at last contact will be censored. End of study will be defined as 2 years after the last patient is randomized. The primary endpoint will be compared between groups using the intent-to-treat principle.

A secondary endpoint of the study is **relapse-free survival** (RFS) from the time of randomization, to be compared between groups with the stratified log-rank test. For descriptive purposes, we shall also report survival and RFS estimates from time of transplant among patients who receive a transplant. Patients alive without relapse at last contact will be censored for RFS.

[figure not shown]
A secondary objective of the study is to compare the **rate of transplantation** among patients with MRD following intensive chemotherapy. The proportion of patients who were transplanted will be compared between arms using the chi-square test

A secondary objective of the study is to examine the **types of transplant** received following treatment with CPX-351 as compared to patients receiving immediate transplantation. Among patients receiving transplantation, the proportion of patients in each arm receiving myeloablative transplant conditioning will be compared using the chi-square or Fisher's exact test. Among patients receiving transplantation, the proportion of receiving donor stem cells from a haploidentical donor, an unrelated donor, or from cord blood unit will be compared across arms using the chi-square or Fisher's exact test.

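### Sections 3.3.2 and 17.2 define the secondary endpoint RFS from different starting dates and disagree on whether RFS from transplant is compared between arms or only described

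*Combined protocol and SAP*

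**What the plan says.** Section 3.3.2 (Secondary Endpoints) starts RFS at the finding of residual disease and says that two comparisons will be carried out. The first is the "number of days elapsing between the date of MRD identification and the date of death or relapse". The second is, "among transplanted patients, the number of days elapsing between the date of transplantation and the date of death or relapse".

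Section 17.2 (Primary/Secondary Endpoints, Objectives and Analytical Methods) specifies relapse-free survival ("RFS) from the time of randomization, to be compared between groups with the stratified log-rank test". It censors patients alive without relapse at last contact. On the transplanted subset it says: "For descriptive purposes, we shall also report survival and RFS estimates from time of transplant among patients who receive a transplant".

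The synopsis and section 3.1.2 name RFS without a starting date, so they do not settle the matter. Overall survival has no such conflict: sections 3.3.1 and 17.2 both start it at randomization.

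**The concern.** Both sections are current text and no clause ranks them. Two analysts working from the same data could each follow the protocol and report different RFS medians and 12-month rates.

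The second disagreement matters more for inference. Transplantation happens after randomization, and the assigned arm is expected to influence whether and when it happens. For Arm A, section 8.2 says: "It is the intent of the study that patients randomized to treatment ARM A begin transplant conditioning within 45 days of randomization". For Arm B, section 8.3 schedules conditioning within 60 days of the most recent chemotherapy cycle, and after a second cycle "the expected time frame for start of HCT conditioning regimen will be considered within 60 days from CPX-351 Cycle 2, Day 1". Section 11.1 adds that "it is possible that use of CPX could lead to an unacceptable fraction of patients who do not proceed to transplant". Patients who reach transplant in the two arms are therefore selected differently, and their clocks start at different times after randomization. A between-arm comparison in that subset is not a randomized comparison. Section 3.3.2 as written calls for one; section 17.2 does not.

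**Working it through.** The plan states no RFS rate, power or event count for this trial, so there is no figure of its own to reproduce. The check sets the two sections side by side and then sizes the consequences under stated assumptions.

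**1. Are the starting dates really different?** Yes. Under section 8.1 a patient is randomized only after a marrow shows MRD, so MRD identification comes first. The gap is not given. The 90-day window in section 5.1.1 runs between chemotherapy and MRD detection and does not bound it.

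**2. Effect on the estimate.** Inputs:
- 12-month RFS of 20% from randomization. This is an assumption, borrowed from the cohort of MRD-positive transplant recipients cited in section 2.2.2.
- A constant hazard (assumption).
- A gap g of 14 or 30 days (assumption).

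No event can be counted during the gap, so 12-month RFS from MRD identification equals RFS at 365 − g days from randomization.
- Hazard: h = −ln(0.20) = 1.609 per year.
- g = 14: exp(−1.609 × 351/365) = 0.213, that is 21.3%, up 1.3 points.
- g = 30: exp(−1.609 × 335/365) = 0.228, that is 22.8%, up 2.8 points.

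The shift applies to both arms.

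**3. Effect on the between-arm test.** The gap precedes randomization and so is independent of arm. With no treatment difference the arms stay exchangeable and the log-rank test stays valid. A simulation agrees. It used 65 patients per arm, 4,000 runs, exponential RFS with a median of 365 days in the better arm, a hazard ratio of 0.58, censoring uniform over 2 to 5 years, and an unstratified test at two-sided 0.05. The gap was uniform from 0 to a maximum of 0, 14, 30, 60 or 90 days.
- Power: 84.8%, 86.2%, 83.8%, 84.5%, 84.6%.
- Rejection with no difference: 5.5%, 5.9%, 5.4%, 5.2%, 4.2%.

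Power shows no trend with the length of the gap. These are not estimates of the trial's RFS power, because the median is assumed.

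**4. Comparison from transplant.** The documents give neither the share of Arm B that will be transplanted nor the actual timing, so the bias cannot be computed. One illustration shows how it arises. Suppose the arms are identical from randomization. There are two equal-sized risk groups, one with 4 times the hazard of the other, and overall 12-month RFS is 20%:

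S(t) = 0.5 exp(−0.969t) + 0.5 exp(−3.878t), t in years.

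Everyone still event-free is transplanted at day 45 in Arm A or day 60 in Arm B, with CPX-351 assumed to start on the day of randomization. With days as arguments, 12-month RFS from transplant is:
- Arm A: S(410)/S(45) = 23.2%.
- Arm B: S(425)/S(60) = 24.2%.

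The gap of 1.0 point is created entirely by the later start, which removes more high-risk patients from Arm B. Hazard ratios of 2 to 6 between the risk groups give 0.3 to 1.7 points. If 25% or 50% of Arm B had a second cycle and were transplanted at day 120 (60 + 60), the gap would be 1.8 or 2.6 points.

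**The case against.** The strongest reply is that section 17.2 is the statistical section and the only one that gives RFS a test, strata and a censoring rule, so an analyst has just one specification that can be executed. That is the natural reading, and it is a good reason to grade the point low. But the protocol does not say that 17.2 prevails, and 3.3.2 is the section that formally lists the secondary endpoints.

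It can also be said that loss before transplant is not hidden. Transplantation is a secondary endpoint compared by chi-square test, with a log-rank comparison of time to transplant in 3.3.2, and RFS under 17.2 counts events before transplant. This stands.

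The modelled gaps of 1.0 to 2.6 points are small. Under the same model about 39 to 49 patients per arm remain, and the standard error of the difference is about 9 points (binomial approximation, no censoring). The model also treats scheduling limits as actual transplant days, and its mix of risk groups has no source in the documents. This stands too: the illustration shows a mechanism, not an expected size.

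Three stronger readings are tempting but unsupported.
- A reader might infer from section 2.2.3 that the starting date changes the conclusion, since 16 chemotherapy-then-transplant patients did not differ significantly from 80 direct-transplant patients from the earlier date but did worse from transplant (medians 4.4 vs 10.4 months, p = 0.02). Both contrasts are limited to transplanted patients. The contrast closest to 17.2, all 49 chemotherapy patients against the 80, points the same way as the from-transplant result (11.6 vs 13.8 months, p = 0.01). The data are also non-randomized and concern overall survival.
- A reader might infer how many of Arm B would be left out, either from the retrospective remark that "only 16/49 patients who received chemotherapy to reduce MRD prior to HCT subsequently received HCT" or from the 20% failure rate in section 17.5. The retrospective group received varied regimens, whereas this trial requires an identified donor and transplant eligibility. The 20% is a suspension trigger, not a cap; it also counts delays and excludes failures not due to toxicity.
- A reader might take the lack of a named RFS test in 3.3.2 as a sign that inference is intended. Silence does not show that. The conflict rests on 3.3.2 calling the from-transplant analysis a comparison.

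**Conclusion.** The contradiction is real and lies in current text: two starting dates for the same secondary endpoint, and two statuses for RFS from transplant. The starting date changes the reported estimates, by 1.3 to 2.8 points at 12 months for assumed gaps of 14 to 30 days and a constant hazard giving 20%, and has little effect on the between-arm test. The from-transplant comparison in 3.3.2 lacks the protection of randomization; the documents do not fix the size or direction of any bias, and it may be small. The primary overall-survival analysis and the sample size are untouched, and the RFS analysis in 17.2, if followed, starts at randomization. Severity is minor. The textual conflict does not depend on any assumption; only the sizes do.

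**What to change.** Rewrite the RFS item in section 3.3.2 to match 17.2:
- RFS runs from randomization to relapse or death, in all randomized patients, compared by the stratified log-rank test.
- RFS from transplant is reported by arm as a description, with no between-arm test.

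Add one sentence to 17.2 saying that the from-transplant estimates will be shown next to the number of patients in each arm who were not transplanted.

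The cost is a wording edit in 3.3.2 and one sentence in 17.2. Sample size, data collection and the primary analysis do not change. Because the trial is open-label, the edit is best made before RFS is analysed by arm.
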